### 9.2.1. Inclusion criteria

Patients must meet all of the following inclusion criteria to be eligible to the study:

1. Patient  $\geq 18$  years of age
2. Patient with locally advanced or metastatic urothelial carcinoma (irrespective of tumor histology) whose disease has not progressed (ongoing stable disease, partial response or complete response) following completion of first-line platinum-based chemotherapy and who has been (retrospective), is (retrospective and prospective), will be (prospective) treated with avelumab.
3. For a patient alive at the moment of the inclusion in the study : the patient must be informed of the study, he/she must be given an information letter signed by the investigator and must not be opposed to the collection of his/her data

For a patient who died before the inclusion in the study : the patient (during his lifetime) must not be opposed in writing to the collection of his data. 4. Patient benefiting from a social security scheme according to local regulations

### 9.2.2. Exclusion criteria

Patients meeting any of the following criteria will not be included in the study:

5. For a patient alive at the moment of the inclusion in the study: patient without liberty, under tutelage, or unable to give oral consent.
6. Patient enrolled in a prospective interventional clinical trial assessing an investigational product.

### 9.3. Variables

Table 2 shows the information which will be collected in the study.

090177e1a41aac13\Final\Final On: 28-Jul-2025 13:50 (GMT)

Table 2. Information collected in the study and timing of data collection

Data elements	Variables	Timing of data collection		
		Inclusion	6 weeks	3 months, then every three months until end of follow-up
Inclusion	
 
Type of center
 
Eligibility criteria (inclusion/exclusion)
 
Date of provision of information letter
 
	X		X
Characteristics of patients and their cancer before avelumab initiation	
 
Demographics : month and year of birth, sex
 
Patient and Cancer characteristics: 
 
Localisation: upper/lower (bladder, urethra) urinary tract
 
Cancer characteristics: histological subtype including type of variant*, PD-L1 status and FGFR alteration with type of test and CPS score.
 
 
 
Localized cancer: date of diagnosis, type of treatment (adjuvant/neoadjuvant), regimen, dates of start and end, number of ChT cycles, complete response if neoadjuvant.
 
Adv/mUC: date of diagnosis, stage at ChT initiation, metastatic sites at ChT initiation, Karnowski index and ECOG at ChT initiation, type of ChT regimen, dates of start and end, number of ChT
 
	X		X

090177e1a41aac13\Final\Final On: 28-Jul-2025 13:50 (GMT)

	cycles, response at the end of ChT, date of start of partial or complete response if so.			
Initiation of avelumab	
 
• Patients characteristics : ECOG at initiation
 
• Biological exam: neutrophil, lymphocyte, haemoglobin, creatinine clearance
 
• Metastatic sites
 
• Date of first administration, dose
 
• Use of premedication (acetaminophen and antihistamine)
 
	X		X
Clinical Follow-up data	
 
• Avelumab administration               
 
. Date of each infusion, dose
 
. Use of premedication (acetaminophen and antihistamine)
 
 
 
• Tumoral response under avelumab               
 
. At inclusion (for retrospective data collection): tumoral evaluation (yes/no), best response since avelumab initiation, date of partial or complete response if so, date of progression if so with site(s) of progression and type (new or preexisting lesions).
 
. Tumoral evaluation since last visit (yes/no, date), response (partial remission, complete remission, progression, stable disease, not evaluable), site(s) of progression if so and type (new or preexisting lesions).
 
 
 
• ECOG if the patient is still on avelumab
 
• Avelumab discontinuation
 
	X		X

090177e1a41aac13\Final\Final On: 28-Jul-2025 13:50 (GMT)

	
 
. Temporary interruption(s) with reason and dates
 
. Permanent discontinuation with reason and date
 
• Subsequent treatments after avelumab discontinuation
 
. Regimen and dates start/discontinuation
 
. Best response, progression with date,
 
• Death with date and cause
 
• Lost to follow-up if so and date
 
• Date of withdrawal if so
 
			
Safety	Adverse events (see section 11)	X		X
Concomitant treatments	Corticosteroids/AIS/NSAIDs, sartans/ACE inhibitors, antibiotics, PPI, if the patient is still on avelumab	X		X
Patient reported outcome (PRO)	
Patients initiating avelumab after the start of the study will complete NCCN/FACT FBISI-18 and EQ-5D-5L questionnaires:
 
 
1) at the time of avelumab initiation (baseline)
 
2) at different time points after initiation if the patient is still treated with avelumab : 6 weeks, 3 months, every three months for up to 2 years, tumor progression if so
 
3) at avelumab discontinuation (whatever the reason is)
 
	X	X	X

\* In order to validate the type of variants, anonymized anatomical pathology reports of the patients concerned will be collected and reviewed by the steering committee.

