- Other subgroups of interest: ECOG at avelumab initiation (PS 0-1; PS  $\geq$ 2), locally advanced urothelial carcinoma versus metastatic urothelial carcinoma, previous ChT regimens (Cis/Gem, Carbo/Gem, Cis/Carbo/Gem, MVAC regimens, others), best response to 1st line chemotherapy (CR, PR, SD; CR+PR, SD), number of ChT cycles received in 1st line (< 4 cycles;  $\geq$  4 cycles and  $\leq$  6; > 6 cycles), site of baseline metastases before ChT (visceral vs non-visceral), patients with an early relapse on avelumab (progression at the first tumoral assessment) and patients with a long-term response to avelumab (4th quartile), delay between the end of ChT and the start of avelumab (< 4 weeks; between 4 and 10 weeks; >10 weeks), ATU patients versus non ATU patients, site for the primary tumor (bladder, urethra, upper tract), PD-L1 status, FGFR abnormality, Bajorin risk classification evaluated before ChT 1st line (0, 1, 2), presence of biological anomalies (neutropenia, lymphopenia, impaired renal function, anemia), use of concomitant treatments (corticosteroids/AIS/NSAIDs, sartans/ACE inhibitors, antibiotics, PPI) at avelumab initiation.

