## 9. RESEARCH METHODS

### 9.1. Study design

Multicenter ambispective (retrospective and prospective) non-interventional study of adv/mUC patients treated with avelumab, not impacting the treatment decision made by the treating physician and the medical management of treated patients (Figure 1).

Inclusion period: expected 18 months to reach sample size.

Target sample size is 600 patients.

- All patients who initiated avelumab before the start of the study in the site will be included retrospectively. All patients are eligible: those under avelumab at inclusion, those who died before the start of the study, and those no longer treated with avelumab at the time of the study start.
- Patients initiating the drug after the start of the study in the site will be prospectively included.

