#### Patients selection

In order to limit the selection bias of study patients, participating centers will be asked to include retrospectively all eligible patients from their center who had already initiated a treatment with avelumab for adv/mUC, and for the prospective part of the study, to consecutively enroll all eligible patients after study set-up, until the planned number of patients have been included in the study. All patients who died before study set-up will be included, to avoid survival bias.

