5.3 SUBGROUPS

The primary and secondary objectives will be evaluated on the overall population and for prespecified subgroup.

- Main subgroup of interest: histology (UC with variant; UC without variant).
- Other subgroups of interest:
 - Histology (Pure UC; UC with variant, Pure adenocarcinoma, Other, Missing)
 - ECOG at avelumab initiation (PS 0-1; PS ≥ 2),
 - Locally advanced urothelial carcinoma versus metastatic urothelial carcinoma,
 - Previous ChT regimens (Cis/Gem, Carbo/Gem, Cis/Carbo/Gem, MVAC regimens, others),
 - Best response to 1st line chemotherapy (CR, PR, SD)
 - Regrouped best response to 1st line chemotherapy (CR+PR, SD),
 - Number of ChT cycles received in 1st line (< 4 cycles; ≥ 4 cycles and ≤ 6 ; > 6 cycles), Site of baseline metastases before ChT (visceral vs non-visceral),
 - Participants with an early relapse on avelumab and participants with a long-term response to avelumab. Patient is considered as early progressor if PFS is less than 3 months and if progression is observed. Patient is considered as long responder if PFS is equal or higher than 12 months, whatever the outcome.
This subgroup of interest will be used only for Overall Survival and progression free survival analyses, and baseline characteristics.
 - Delay between the end of ChT and the start of avelumab (< 4 weeks; between 4 and 10 weeks; > 10 weeks),
 - Delay between the end of ChT and the start of avelumab (< 4 weeks; ≥ 4 weeks),
 - ATU participants versus non ATU participants, site for the primary tumor (bladder, urethra, upper tract),
 - PD-L1 status,
 - FGFR abnormality,
 - Bajorin risk classification evaluated before ChT 1st line (0, 1, 2),
 - Presence of biological anomalies (neutropenia, lymphopenia, impaired renal function, anemia),
 - Use of concomitant treatments (corticosteroids/AIS/NSAIDs, sartans/ACE inhibitors, antibiotics, PPI) at avelumab initiation,
 - Type of subsequent treatment: Antibody-Drug Conjugate (ADC) treatment, chemotherapy, immunotherapy, targeted therapy, other. This classification will be made thanks to a medical review from Pfizer team.
 - Type of subsequent treatment: ADC versus Other.

PFIZER CONFIDENTIAL

CT24-WI-GL03-RF02 2.0 Non-Interventional Statistical Analysis Plan For Primary Data Collection Study

01-Jun-2020

Page 11 of 28

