6.1.2 Objective response rate (ORR)

Best response will be calculated with all available response assessments, from study treatment initiation to treatment discontinuation (included) or end of study if no discontinuation.

PFIZER CONFIDENTIAL

CT24-WI-GL03-RF02 2.0 Non-Interventional Statistical Analysis Plan For Primary Data Collection Study

01-Jun-2020

Page 13 of 28

For best response, the following order will be used (from better outcome to worst)
Complete Response (CR) > Partial Response (PR) > Stable Disease (SD) > Not Estimable (NE) > Progressive Disease (PD).

6.1.3 **FBISI-18 score**

NCCN-FACT FBISI-18 is an 18-item questionnaire filled by the participant. The response to each of the 18 questions is evaluated using a 5-point scale ranging from 0='Not at all' to 4='Very much'. For items negatively framed, scores will be reversed for analysis so that higher scores translate a good quality of life.

6.1.4 **EQ-5D-5L score**

A participant's score at a specific timepoint will then go from 0 (0=severely symptomatic) to 72 (asymptomatic). For each participant, a unique Health state score will be created by combining the answer given to each of the 5 dimensions. This score will thus be ranging from 11111 (no problems in any domain) to 55555 (severe problems). This score will be after converted into EQ-5D single utility index values anchored at 0 for death and 1 for perfect health, by applying a formula download from the EQ-5D official website, that essentially attaches values (also called weights) to each of the levels in each dimension.

6.2 **SAFETY ENDPOINTS**

Adverse events (AE) reported during the study will be coded using the MedDRA terminology (SOC and PT) with the most recent version of MedDRA.

6.3 **COVARIATES**

Refer to [5.3](#).

7 **HANDLING OF MISSING VALUES**

Unless otherwise specified, all data will be evaluated as observed, and missing data will not be imputed.

- The objective response will be the only endpoint with a formal imputation of missing data. Participants who do not have a post-baseline radiographic tumour assessment due to early progression, who receive anti-tumour therapies other than the study treatments prior to reaching a CR or PR, or who die, progress, or drop out for any reason prior to reaching a CR or PR will be counted as non-responders in the assessment of OR. Each participant will have an objective response status (0: no OR; 1: OR).

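### Table 2 collects concomitant treatments only while a patient is on avelumab, so the subgroup defined by use at initiation would leave out retrospective patients who died or stopped before inclusion

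*Protocol*

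**What the plan says.** Protocol section 8 lists among the subgroups "use of concomitant treatments (corticosteroids/AIS/NSAIDs, sartans/ACE inhibitors, antibiotics, PPI) at avelumab initiation". The same section names it as a patient characteristic to describe. SAP section 2.2 repeats the description objective, and SAP 5.3 repeats the subgroup: "Use of concomitant treatments (corticosteroids/AIS/NSAIDs, sartans/ACE inhibitors, antibiotics, PPI) at avelumab initiation". SAP 8.2.1 and 8.2.2.2 describe OS and PFS by the 5.3 subgroups, and SAP 8.1.3 compares subgroup levels by univariate Cox models.

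The data come from Protocol Table 2 (section 9.3). Its only row for these drugs reads "Corticosteroids/AIS/NSAIDs, sartans/ACE inhibitors, antibiotics, PPI, if the patient is still on avelumab" and is marked at inclusion and every three months. The row for avelumab initiation covers performance status, blood tests, metastatic sites, first dose and "Use of premedication (acetaminophen and antihistamine"), with no concomitant treatments.

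The retrospective part takes in "those who died before the start of the study, and those no longer treated with avelumab at the time of the study start" (Protocol 9.1). Section 9.9.1 gives the reason: "All patients who died before study set-up will be included, to avoid survival bias". On missing data, SAP section 7 states: "Unless otherwise specified, all data will be evaluated as observed, and missing data will not be imputed". Protocol 9.9.2 also says that missing data are not replaced, and SAP 8.2.5 lists them as excluded.

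**The concern.** The subgroup is fixed at the first dose, but the only scheduled collection depends on being on avelumab at a later date. For a prospective patient the two dates nearly coincide. A retrospective patient must have survived and stayed on treatment until inclusion to get a value. The patients brought in to prevent survival bias would then drop out of this one analysis.

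OS and PFS are counted from the first injection, so retrospective patients who remain in the subgroup bring a stretch of time in which they could not have died or stopped. The SAP handles left truncation only for OS from the start of chemotherapy (8.1.3 and 8.2.2.1), so nothing corrects for this here. The survival curves for users and non-users of steroids, antibiotics or PPI would sit above those of the cohort they are meant to describe.

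**Working it through.** **Step 1: set the items side by side.** Performance status appears twice in Table 2: unconditionally in the initiation row, and again at follow-up as "ECOG if the patient is still on avelumab". Concomitant treatments have only the conditional item. The table therefore knows how to separate a baseline value from its updates, and does not do so here.

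**Step 2: who has a value if Table 2 is followed literally.**
- Included at initiation (prospective): yes, at the right time.
- Retrospective, still on avelumab at inclusion: yes, but entered after the first dose.
- Retrospective, dead or off avelumab at inclusion: no.

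**Step 3: check the survival model.** Protocol 9.5 takes exponential OS with mean 29 months, so the median is 29 × ln 2 = 20.1. The exact interval, median × 2n/χ²(0.975; 2n) to median × 2n/χ²(0.025; 2n), gives [18.6; 21.8] for n = 600 and [15.4; 27.4] for n = 47. Both agree with the protocol. They do not bear on this point beyond confirming the model, which is used below with the stated 20-month median.

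**Step 4: size of the selection in retrospective patients.**

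From the documents: OS exponential, median 20 months, so λ = ln 2/20.

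Assumed, because the documents do not give them: time to stopping avelumab exponential with median m = 4, 6 or 9 months (μ = ln 2/m), independent of death; lag from first dose to inclusion uniform on 0 to L, with L = 6 or 12 months. The lag range fits an ATU from July 2020 and data collection from Q2 2021.

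A value exists if both death and stopping fall after the lag.
- Share with a value: B = (1 − e^(−(λ+μ)L)) / ((λ+μ)L)
- Chance of not having stopped by inclusion: A = (1 − e^(−μL)) / (μL)
- 12-month OS given a value: 2^(−0.6) × A/B, against 2^(−0.6) = 66% for everyone
- Median OS given a value: 20 + 20 × log₂(A/B)

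| m | L | A | B | 12-month OS | Median OS |
|---|---|---|---|---|---|
| 4 | 6 | 0.622 | 57% | 72% | 22.4 |
| 4 | 12 | 0.421 | 37% | 76% | 23.9 |
| 6 | 6 | 0.721 | 66% | 72% | 22.6 |
| 6 | 12 | 0.541 | 46% | 77% | 24.5 |
| 9 | 6 | 0.801 | 73% | 72% | 22.7 |
| 9 | 12 | 0.653 | 55% | 78% | 24.9 |

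**Step 5: pooled with prospective patients.** Let w be the retrospective share, assumed 30% or 50%. The share of the cohort with a value is 1 − w + wB, which runs from 0.5 + 0.5 × 0.368 = 68% to 0.7 + 0.3 × 0.729 = 92%. So 8–32% of the cohort leaves the subgroup. Pooled 12-month OS is 66% × (1 − w + wA)/(1 − w + wB), which runs from 67% to 70%.

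**Step 6: sensitivity to independence.** A simulation with stopping medians of 4 to 12 months, lags up to 6, 9 or 11 months, and a correlation of 0.6 between OS and treatment duration kept 43–80% of retrospective patients. Their median OS was 25.2–32.5 months, and that of the patients left out was 4.2–12.8. Independence is therefore the milder case.

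**The case against.** **Table 2 is a summary, and the CRF is not available.** Its timing marks are not literal: fixed items such as sex and eligibility are also marked every three months. The condition may only say when updating stops, and both documents clearly want use at initiation. This stands as a limit on certainty. The gap is what Table 2 implies, not a proven loss of data. If the CRF does ask, Table 2 still needs correcting.

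**Late entry is not late measurement.** A reader might infer that drugs started during follow-up will be counted as baseline use. The documents do not say so. SAP 11.1.2 has rules for partial medication start and end dates, which implies that dates are recorded. Use at first injection could then be rebuilt for retrospective patients still on avelumab. That cannot help patients with no record, and SAP 5.3 does not say that the dates will be used in this way.

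**Hazard ratios.** A reader might also infer that the Cox comparisons are biased. This is not shown. In an illustrative run (30% exposed, half retrospective, stopping median 6 months, lag 0–12 months, stopping unrelated to exposure, exposure correctly dated, crude event-rate ratio to 36 months), a true ratio of 1.0 stayed at 1.00 and a ratio of 1.5 became 1.48–1.49. If stopping depends on exposure the bias could be larger, but neither its size nor its direction can be fixed from the documents.

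**Proportion.** This is one secondary subgroup in a study without formal hypotheses (SAP 4.1, 4.2). The pooled shift of 1 to 4 points is of the same order as the sampling half-width at n = 600: 1.96 × √(0.66 × 0.34/600) = 3.8 points. That is a fair reason not to rank the point higher. The shift is systematic, however, and no confidence interval would show it.

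**Conclusion.** The point holds at moderate severity. As Table 2 is written, a value for use at initiation exists for a retrospective patient only if that patient survived and stayed on avelumab until inclusion, and no rule in the SAP corrects for it. Absolute OS and PFS in this subgroup would be too favourable. For OS, under independence and the assumed stopping times and lags, that means 72–78% at 12 months against 66% in retrospective patients with a value, and 67–70% pooled if 30–50% of the cohort is retrospective. The direction follows from the selection itself; the size rests on stopping times, lags and a retrospective share that the documents do not give.

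It would be wrong to extend this further. Prospective patients are measured on time. Primary OS in the FAS and the histology subgroup do not use this variable. Late recording concerns only retrospective patients still on avelumab, and only if medication dates go unused.

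**What to change.** 1. In Table 2 and the eCRF, add to the initiation row an item for concomitant treatments at avelumab initiation, with start and end dates, for every patient whatever their treatment or vital status. Keep the still-on-avelumab condition for follow-up updates only. If the CRF already collects this, correct Table 2 to say so.
2. In SAP 5.3, define use as ongoing on the date of first injection (start on or before, end on or after).
3. Report the number missing for this variable separately for retrospective and prospective patients.
4. If back-collection is not feasible, restrict this subgroup to patients included at initiation and say so. Delayed entry at inclusion is the other option. It removes the guaranteed time, but the result still describes only patients who were on avelumab at inclusion, and this should be stated.

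Cost: items 1 and 2 need one eCRF item, one SAP sentence and a protocol amendment with CPP authorisation. They also need further chart abstraction for retrospective patients across about 100 expected sites, some of it from closed files, since version 6.0 dates from late in the planned inclusion period. Restricting the subgroup needs no new data, but the subgroup is smaller.

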  - The EQ VAS records the patient's self-rated health on a vertical visual analogue scale, where the endpoints are labelled 'The best health you can imagine' and 'The worst health you can imagine'. The VAS can be used as a quantitative measure of health outcome that reflect the patient's own judgement.

## 9.5. Study size

The primary endpoint is the Overall Survival (OS). In this non-interventional study, the objective is only descriptive and the sample size will rely on the precision of the estimate.

The expected precision of the median survival time can be calculated using following assumptions:

- Expected median Overall Survival time: 20 months.
- Two-sided 95% Confidence Interval (CI).
- Exponential Lifetime Percentile distribution ( $S(t)=e^{-t/29}$ ) with a median survival time of 20 months and a mean survival of 29 months.
- Assuming the absence of right-censoring before the median survival and the occurrence of a single event for each event time.

The different accuracies and CI for the median overall survival time can therefore be calculated as a function of sample sizes. Below accuracy and 95%CI for a median survival time of 20 months:

Total Sample size	Accuracy (total patients)	Lower CI	Upper CI
400	4,0	18,3	22,2
433	3,8	18,3	22,1
467	3,7	18,4	22,1
500	3,5	18,4	22,0
533	3,4	18,5	21,9
567	3,3	18,5	21,9
600	3,2	18,6	21,8
667	3,1	18,7	21,7
800	2,8	18,8	21,6
1000	2,5	18,9	21,4

With 600 patients, the CI of OS is expected to be [18.6; 21.8] for a 3.2 months accuracy.

A total of 47 variant patients for a total sample size of 600 patients will produce a two-sided 95% confidence interval for the median survival time with a width equal to 12 months (PASS® version 15.0 validated with Nquery® version 8.3.1 - reference Mathews, Paul. 2010. Sample Size Calculations: Practical Methods for Engineers and Scientists. Mathews Malnar and Bailey, Inc.).

With a total of 47 patients, the two-sided 95% CI associated to a median survival time of 20 months will be [15.4 ; 27.4]. Of note the two-sided 95% CI for the whole sample (600 patients) will be [18.6 ; 21.8].

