2.1 STUDY DESIGN

Multicenter ambispective (retrospective and prospective) non-interventional study of adv/mUC patients treated with avelumab, not impacting the treatment decision made by the treating physician and the medical management of treated patients (Figure 1: Study design).

Inclusion period: expected 18 months to reach sample size.

Target sample size is 500 patients.

1. All patients who initiated avelumab before the start of the study in the site will be included retrospectively. All patients are eligible: those under avelumab at inclusion, those who died before the start of the study, and those no longer treated with avelumab at the time of the study start.
2. Patients initiating the drug after the start of the study in the site will be prospectively included.

Follow-up:

The last patient prospectively included will be followed for 2 years. All other patients will be followed until death or until the end of the follow-up of the last patient prospectively included.

Patients who started avelumab before the start of the study will be followed retrospectively, but also prospectively for those still alive at the beginning of the study.

Follow-up visits will be made during the course of regular visits and/or hospitalizations. No additional visits or examinations are required by the protocol, as the study is observational: follow-up and treatment modalities will be at the sole discretion of the participating physician.

Clinical data will be collected every three months after the inclusion in the study and until death or the end of the study: 24 months after the inclusion of the last prospective patient.

Patients initiating avelumab after the start of the study (prospective part of the study) will complete PRO questionnaires: 1) at the time of avelumab initiation, 2) at different time points after initiation if the patient is still treated with avelumab (6 weeks, 3 months, and every three months for up to 2 years, tumor progression if so), 3) and at avelumab discontinuation.

Number of sites: the study will be proposed to all sites participating to the ATU program, plus some additional centers expected to treat patients after the ATU period. Approximately 100 sites are expected to participate to the study.

PFIZER CONFIDENTIAL

CT24-WI-GL03-RF02 2.0 Non-Interventional Statistical Analysis Plan For Primary Data Collection Study

01-Jun-2020

Page 7 of 28

[figure not shown]

Figure 1: Study design

Study population:

Inclusion criteria

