8.1.3 Analysis of time-to-event data

Kaplan-Meier estimates (product-limit estimates) will be presented together with a summary of associated statistics including the median survival time with 2-sided 95% CIs. In particular, the survival rate at 3, 6, 9, 12, 15, 18 and 24 months will be estimated with corresponding 2-sided 95% CIs. The CIs for the median will be calculated according

PFIZER CONFIDENTIAL

CT24-WI-GL03-RF02 2.0 *Non-Interventional Statistical Analysis Plan For Primary Data Collection Study*

01-Jun-2020

Page 15 of 28

to Brookmeyer and Crowley (Brookmeyer R, 1982) and the CIs for the survival function estimates at the time points defined above will be derived using the log-log transformation according to Kalbfleisch and Prentice (Kalbfleisch JD, 2002) (conftype=loglog default option in SAS Proc LIFETEST) with back transformation to a CI on the untransformed scale. The estimate of the standard error will be computed using Greenwood's formula.

Frequency (number and percentage) of participants with each event type and censoring reasons will be presented.

For each subgroup analysis, comparison of the different modalities to a reference level will be performed using univariate Cox proportional hazard models. Ties will be handled using the Exact option in SAS (Ties=Exact option in SAS PROC PHREG). Results will be expressed in terms of hazard ratios (HR) and a 2-sided 95% CI will be associated to each HR. A HR of 1 equals a lack of association, a HR greater than 1 suggests an increased risk compared to the reference level, and a HR below 1 suggests a decreased risk.

Time of follow-up for each event (OS and PFS)

A Kaplan-Meier estimation for follow-up duration will also be generated to assess the follow-up time reversing the censoring and event indicators.

Handling of left truncation and right censoring:

The overall survival from the first injection of the chemotherapy used in 1st line will cover

a retrospective and/or prospective data collection period. The time to event of interest ("survival" time) or censoring if no event occurs (right censoring) will be based on the 1st line of chemotherapy start date at a time-point preceding the study entry (avelumab start date). As a result, only participants who are still alive are included in the study.

Therefore, the time from 1st line of chemotherapy start date to avelumab start date is called immortal time and corresponds to a left truncation in survival analyses.

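### The precision promised for median OS (3.2 months for 600 patients, 12 months for 47 variant patients) belongs to an exponential formula with every death observed; the planned Kaplan-Meier analysis gives about 4.6 and 16–17 months

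*Protocol*

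**What the plan says.** Protocol 9.5 (Study size) states that the study is descriptive and that the sample size rests on the precision of the estimate. Its planning inputs are:

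- "Expected median Overall Survival time: 20 months";
- a two-sided 95% interval;
- an exponential curve S(t) = exp(−t/29), "with a median survival time of 20 months and a mean survival of 29 months";
- on censoring and ties, the condition "Assuming the absence of right-censoring before the median survival and the occurrence of a single event for each event time".

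A table of ten sample sizes follows. The conclusion for the whole cohort is "With 600 patients, the CI of OS is expected to be [18.6; 21.8] for a 3.2 months accuracy". For the main subgroup the claim is "A total of 47 variant patients for a total sample size of 600 patients will produce a two-sided 95% confidence interval"; its width is put at 12 months, from 15.4 to 27.4.

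The planned analysis is set out elsewhere. Protocol 9.7 and SAP 8.2.1 specify Kaplan-Meier for OS, with patients alive censored at last contact. On the interval itself, SAP 8.1.3 has a sentence that begins "The CIs for the median will be calculated according"; the method it names is Brookmeyer-Crowley, which is non-parametric. Neither document plans a parametric exponential analysis of OS.

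On the target, protocol V6.0 (21 November 2022) sets 600 patients. SAP 2.1 (2 December 2022) still reads "Target sample size is 500 patients".

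**The concern.** A precision calculation should describe the interval that will be reported. An interval that assumes an exponential shape draws on every death over the whole curve. A Kaplan-Meier interval for the median uses only the local information around the point where survival crosses one half, so it is wider at the same sample size. If the 9.5 figures come from the first kind, the planned analysis will not deliver them, even with complete follow-up.

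This matters because precision is the only basis for the sample size. The amendment log says V6.0 raised the target to 600 to reach the variant number planned at the outset. Protocol 9.5 attaches the 12-month width to 47 variant patients, and histology is the main subgroup of interest.

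**Working it through.** **Step 1. Reproduce the protocol's figures.** Inputs from protocol 9.5: mean 29 months, so the median is 29 × ln 2 = 20.10 months; two-sided 95%. The exact interval for an exponential median with n observed deaths is

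lower = 20.10 × 2n / χ²(0.975; 2n), upper = 20.10 × 2n / χ²(0.025; 2n).

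- n = 600: 20.10 × 1200/1297.9 = 18.59 and 20.10 × 1200/1105.9 = 21.81; width 3.23 (stated 18.6, 21.8, 3.2).
- n = 47: 20.10 × 94/122.7 = 15.40 and 20.10 × 94/69.07 = 27.36; width 11.96 (stated 15.4, 27.4, 12).
- Other rows agree as well, for example 400: 18.27–22.23; 500: 18.45–21.99; 1000: 18.91–21.41. All ten rows match to the printed decimal.

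**Step 2. What that formula requires.** The degrees of freedom are twice the number of deaths, so 2n means that all n patients have died. With only n/2 deaths, as at the median, the same formula gives 17.92–22.47 (width 4.55) for 600 and 13.86–31.38 (width 17.52) for 47. The stated assumption, no censoring before the median, is therefore weaker than what the figures need.

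Complete ascertainment is not expected. With mean θ = 20/ln 2 = 28.85 and follow-up uniform from 24 to U months, the expected share of deaths is 1 − [θ/(U − 24)] × [exp(−24/θ) − exp(−U/θ)].

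- U = 42 (18 months of inclusion plus 24, protocol 9.1): 1 − (28.85/18) × (0.4353 − 0.2333) = 0.676, about 406 of 600.
- U = 54 (assumed, to allow for patients who started earlier): 1 − (28.85/30) × (0.4353 − 0.1539) = 0.729, about 438 of 600.

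**Step 3. Kaplan-Meier width under the same curve, no censoring.** The standard error of the median is √(0.25/n) / f(median), with density f = 0.5/θ = 0.5/28.85. This equals θ/√n.

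- n = 600: SE = 28.85/√600 = 1.178; width 2 × 1.96 × 1.178 = 4.62.
- n = 47: SE = 28.85/√47 = 4.209; width 2 × 1.96 × 4.209 = 16.5.

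The parametric standard error with all deaths observed is median/√n, so the ratio is θ/median = 1/ln 2 = 1.44. This loss comes from the estimator alone, before any censoring.

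**Step 4. Check by other routes.**

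| Method | n = 600 | n = 47 |
|---|---|---|
| Stated in 9.5 | 18.6–21.8 (3.2) | 15.4–27.4 (12) |
| Brookmeyer-Crowley inversion, linear | 17.8–22.4 (4.63) | 12.7–29.7 (17.0) |
| Brookmeyer-Crowley inversion, log-log | 17.7–22.4 (4.62) | 12.3–29.1 (16.8) |
| Order statistics | 17.8–22.5 (4.7) | 12.8–30.5 (17.7) |
| Simulation, no censoring, log-log (mean width) | 4.64 | 16.05 |
| Simulation, no censoring, linear (mean width) | 4.52 | 15.0 |
| Simulation, follow-up 24–42 months, log-log (median width) | 4.59 | 16.4 |
| Simulation, follow-up 24–54 months, log-log (median width) | 4.57 | 16.2 |

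With 24–42 months of follow-up, the upper limit for 47 patients is not reached in about 14% of runs. Adding an assumed 10% loss per year (the documents give no rate) raises the median widths to about 4.8 and 17–18 months, and the upper limit for 47 is then missing in 22–24% of runs.

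**Step 5. Sample size for the stated widths.** Width scales as 1/√n. A 3.2-month Kaplan-Meier width would need 600 × (4.62/3.2)² ≈ 1,250 patients. A 12-month width would need 47 × (16.5/12)² ≈ 89 variant patients.

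**The case against.** The strongest reply is that nothing downstream depends on these numbers. The study has no hypothesis test and no decision rule (SAP 4.1 and 4.2), and the final interval will be computed from the data by a valid method. The protocol also names its exponential model, and its arithmetic is correct for that model. All of this stands: the fault is a mismatch between planning formula and planned estimator, and no power or type I error is lost. But disclosing the model does not tell the reader that the reported interval will come from a different one, and the censoring assumption as printed understates what the figures require.

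A second reply is that a single replacement interval for 47 patients would be too exact. SAP 8.1.3 specifies the log-log transformation for survival rates at fixed times and does not clearly extend it to the median, and the follow-up distribution is assumed. That is fair. The figure for 47 should carry a range and its assumptions, though every variant exceeds 12 months.

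Third, the amendment log does not itself name 47 patients or a 12-month width as the reason for the increase; that link is read from 9.5. Finally, the 500-versus-600 conflict is a separate editorial error that does not affect interval width. It is real, and it is convenient to correct at the same time.

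**Conclusion.** The concern holds. The planned method gives about 4.6 months for 600 patients, so the stated 3.2 is about 30% too narrow (3.2/4.62 = 0.69). For 47 variants it gives about 16–17 months, with roughly 15 to 18 across method variants and censoring assumptions, so the stated 12 is about a quarter too narrow (12/16.5 = 0.73).

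These results rest on the protocol's own exponential curve with a 20-month median. The overall figure hardly depends on administrative censoring, because the minimum follow-up of 24 months exceeds the assumed median. The subgroup figure is less stable, and its upper limit may not be reached. The consequence is overstated precision in the sole rationale for the sample size, chiefly for the main subgroup; the validity of the final estimates is not in question.

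**What to change.** In protocol 9.5, recompute the table for the Kaplan-Meier median with Brookmeyer-Crowley limits under the planned follow-up, and name the transformation and the follow-up and loss assumptions used. For 600 patients, state about 17.7 to 22.4 months (width about 4.6). For 47 variants, state about 12.5 to 29 months (width about 16–17), with the range across assumptions and a note that the upper limit may not be estimable. Remove the 3.2- and 12-month figures as statements of expected precision. If they are kept for reference, label them as parametric values that require every death to be observed.

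In SAP 8.1.3, state the transformation for the interval of the median. In SAP 2.1, change the target to 600.

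The cost is wording and one recalculation. The stated precision becomes less favourable; enrolment, design and analysis method are unchanged.
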